6.2 Visit 2 (screening)

Research Staff

1. CSSA
2. BAL
3. TLFB

4. UBT
5. AE
6. CO
7. Cotinine

Diagnostician

1. Structured Clinical Interview for DSM-IV (SCID) / Mini International Neuropsychiatric Interview (MINI)
2. Hamilton Anxiety Rating Scale (HAM A)
3. Hamilton Depression Rating Scale (HAM D)

6.3 Visit 3 (screening)

Research Staff

1. CSSA
2. BAL
3. UBT
4. TLFB
5. Addiction Severity Index (ASI)
6. AE
7. CO
8. Cotinine

6.4 First visit of each study week during randomized medication phase: Visits 4, 7, 10, 13, 16, 19, 22, 25, 28, 31, 34, 37

All assessments may not be collected at the exact visits specified. Assessments completed weekly will be collected on either the first, second, or third visit of the week. Assessments not completed weekly must be completed within half of the time frame that exists before the next scheduled collection of the assessment.

Nurse or physician

1. Dispense study medications
2. Medical Management session (MM)

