3.3 Secondary Study Endpoints

Secondary Hypotheses:

- We further hypothesize that within the varenicline group, medication compliant participants ($\geq 80\%$ of pills taken) will have higher rates of cocaine abstinence than those who are non-compliant ($< 80\%$ of pills taken).
- We expect that the varenicline group will report less craving for cocaine than will the placebo group, as measured by lower scores on the Cocaine Craving Questionnaire (Tiffany et al., 1993) and the Minnesota Cocaine Craving Scale (Halikas et al., 1991) during the medication treatment phase.
- We expect that the varenicline group will show greater decreases in cigarette smoking than will the placebo group, as evidenced by CO and cotinine levels.

• Primary Safety Endpoints

A nurse or physician will assess for adverse events weekly. Adverse events will be monitored by research staff at all other visits, and the psychiatrist or nurse will be available at other visits to assess the subject if needed. At the conclusion of medications, an end of study physical will be completed and the baseline laboratory tests, including EKG, will be repeated. If the subject is discontinued in treatment due to a serious adverse event, the subject will be followed clinically by medical staff until the adverse experience resolves itself and becomes stable.

4 Subject Selection and Withdrawal

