5.2 Treatment Regimen

Study medication will be initiated in Week 2. The research physician or nurse will explain the dosing regimen and subjects will be randomized to receive either varenicline or placebo. The statistician will randomize subjects to either varenicline or placebo using a computer-generated program of urn randomization, based on specified criteria that are described below.

The dose of varenicline will begin at 0.5 mg daily, and will be titrated up to the target daily dose of 2.0 mg/day at the start of the second week of medication (see Table 1). If adverse events occur, the physician or nurse may keep the dose the same or reduce to fewer pills. If the side effects subside, subjects can be re-challenged or kept at a lower number of pills. During the last week of the medication phase of the trial, varenicline will be reduced to 1.0 mg daily.

Pharmacotherapy will be completed by the end of the 13th week. If tolerated, subjects will be taking the maximum daily dosage (2.0 mg of varenicline or identical appearing capsules) for 10 weeks (Weeks 3-12).

Table 1. Dosing Schedule (taken from package insert)

| Wk. | Daily Dose |
|--------------|---------------------------|
| 2 (days 1-3) | 0.5 mg |
| 2 (days 4-7) | 0.5 mg BID (1.0 mg daily) |
| 3 | 1.0 mg BID (2.0 mg daily) |
| 4 | 1.0 mg BID (2.0 mg daily) |
| 5 | 1.0 mg BID (2.0 mg daily) |
| 6 | 1.0 mg BID (2.0 mg daily) |
| 7 | 1.0 mg BID (2.0 mg daily) |
| 8 | 1.0 mg BID (2.0 mg daily) |
| 9 | 1.0 mg BID (2.0 mg daily) |
| 10 | 1.0 mg BID (2.0 mg daily) |
| 11 | 1.0 mg BID (2.0 mg daily) |
| 12 | 1.0 mg BID (2.0 mg daily) |
| 13 | 0.5 mg BID (1.0 mg daily) |

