11. **Medical history & Physical exam (PE)** A complete medical history and physical exam will be conducted by the nurse or physician at Visit 1. The physical exam will be repeated at visit 40.
12. **Minnesota Cocaine Craving Scale** (MCCS) (Halikas et al., 1991). The MCCS is a valid and reliable measure of cocaine craving. Craving is assessed over three dimensions, intensity, duration, and frequency and subjects are asked to evaluate their craving for the prior week. The MCCS will be administered at baseline, weekly throughout the medication phase of the trial, once at the end of randomized medication phase (Visits 1, 4, 7, 10, 13, 16, 19, 22, 25, 28, 31, 34, 37, 40).
13. **Multiple Choice Procedure (MCP)** (Griffiths, Troisi II, Silverman & Mumford, 1993) This adaptation of the MCP asks participants to choose between a hypothetical static amount of cocaine and hypothetical variable amounts of money. Repeated administrations of the MCP allow for assessment of changes in the relative reinforcing effects of cocaine over time, evidenced by shifts in how much participants are willing to “pay” for a static amount of cocaine (visits 1, 4, 7, 10, 13, 16, 19, 22, 25, 28, 31, 34, 37, 40).
14. **Pill Count** The number of capsules of study medication dispensed and the number returned each week will be recorded in the CRF (visit 4, 7, 10, 13, 16, 19, 22, 25, 28, 31, 34, 37, 40).
15. **Structured Clinical Interview for DSM-IV (SCID) (First et al., 1996), Mini-International Neuropsychiatric Interview (MINI) (Sheehan et al., 2002)** The substance abuse module (Module E) of the SCID-IV will be used to diagnose substance abuse problems. The major depressive episode modules (Modules A and B) of the MINI Plus will be used to diagnosis current and past episodes of major depression and current episodes of major depression with melancholic features. Other lifetime DSM-IV Axis I and II diagnoses will be obtained from the MINI. The SCID/MINI/MINI Plus will be done once during baseline to confirm diagnoses

of cocaine and alcohol dependence and determine if Axis I, Axis II or other substance disorder diagnoses are present. Time of administration will be 45 minutes. The SCID/MINI/MINI Plus will be administered by a clinically-trained Diagnostic Interviewer.

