Initially, we will use these sources to determine whether each subject has complied with their assigned medication for at least 80% of the trial. We will then include a binary variable indicating “80%” compliance in the analyses described above for Hypothesis 1, both as a main effect and as an interaction effect with varenicline group.

We will also use the sources described above to define variables representing compliance/non-compliance over each the 12 weeks of the treatment period. For the primary outcomes, we will perform extensions of instrumental variable regression analyses presented by Nagelkerke et al. (Nagelkerke et al., 2000). Here the instrumental variable is randomization and, under certain assumptions, will control for unmeasured bias when estimating the effect of varenicline relative to placebo in those who comply with their assigned treatment. These analyses will permit a more complete examination of the time-varying effects of compliance across the treatment period.

Hypothesis 3: The CCQ and MCC scales will provide weekly measures of cocaine craving. The scales provide a seven and a six-category Likert response, respectively, and it is likely that we will collapse some adjacent categories prior to the analyses, and regard the responses as ordinal. The analyses for these hypotheses will be perfectly analogous to those for Hypothesis 1, except that mixed-effects models for ordinal responses will be used (Hedeker and Mermelstein, 2000). These analyses will be performed using PROC NLMIXED in SAS.

Hypothesis 4: The CO and cotinine measures will be used to analyze dynamic changes in cigarette smoking, both in isolation and as they relate to cocaine use.

Other Analytic Issues:

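### Visit 4 is labelled a medication-phase visit but is the first dispensing visit; the plan should make its craving scores baseline and name the craving contrast

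*Combined protocol and SAP*

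**What the plan says.** Section 6 makes visits 1-3 the screening period, called Week 1. Section 5.2 states "Study medication will be initiated in Week 2". Section 6.4 then lists "First visit of each study week during randomized medication phase: Visits 4, 7, 10, 13" and every third visit after that up to visit 37, and the first item for the nurse or physician is "Dispense study medications". No dispensing appears at visits 1-3, so visit 4 is the first dispensing visit. The CCQ and MCCS are on the same list.

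The instrument descriptions in Section 6 schedule both scales weekly and at visit 40; for the MCCS the entry ends "once at the end of randomized medication phase (Visits 1, 4, 7, 10, 13, 16, 19, 22, 25, 28, 31, 34, 37, 40". On the MCCS, "subjects are asked to evaluate their craving for the prior week". No recall window is given for the CCQ.

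Section 3.3 places the craving hypothesis "during the medication treatment phase". Section 7.2, Hypothesis 3, says "The CCQ and MCC scales will provide weekly measures of cocaine craving" and carries over the Hypothesis 1 structure (group, time, group by time) in an ordinal mixed-effects model. The only covariates that Section 7.2 specifically proposes are prior alcohol and cocaine use. Baseline craving is not named.

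**The concern.** Read literally, visit 4 is the first craving outcome of the medication phase, although its MCCS score describes time when neither group had received study drug. The expected group difference in that score is zero by randomization. Averaging it with the later scores pulls the estimated craving effect toward zero.

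There is also a dating problem. An MCCS score taken at visit 7 recalls Week 2, and one taken at visit 40 after a completed course recalls Week 13. If each score is filed under the week of its visit, craving is shifted one week against cocaine use. That matters for the analyses under Mechanisms of Action (Section 10.1.b), which use these scales as time-varying covariates and mediators of cocaine use.

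Finally, a pre-dose craving score at visit 4 would be useful as a baseline, and the plan does not assign it that role.

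**Working it through.** **Inputs from the documents.** First-of-week visits 4, 7, ..., 37: 12 visits (Section 6.4). Visit 40 adds one craving score, giving 13 from visit 4 onward. Group size 100 (Section 3.1). Alpha 0.05 and compound symmetry (Section 7.1).

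**Plan's own figure.** The sample size of 200 cannot be reproduced. Section 7.1 gives no effect size, standard deviation, correlation, dropout or power, and no power is stated for craving.

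**Assumptions, for illustration only.** Two-sided test; within-subject correlation r of 0.3, 0.5 or 0.7; unit standard deviation; no dropout; zero effect at visit 4 and a constant effect d afterwards. The effect d is set to give 80% power for the mean of the 12 scores at visits 7-40.

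**Dilution of an average contrast.**
- Visits 4-37: (11 × d + 0)/12 = 0.917 d, a loss of 8.3%.
- Visits 4-40: (12 × d + 0)/13 = 0.923 d, a loss of 7.7%.

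**Power.** The variance of a mean of m scores is v(m) = (1 + (m − 1)r)/m, and z = effect / √(2 v(m)/100). Setting z = 1.960 + 0.842 = 2.802 for visits 7-40 gives d = 0.237, 0.292 and 0.337 for r = 0.3, 0.5 and 0.7.

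| Scores averaged | r = 0.3 | r = 0.5 | r = 0.7 |
|---|---|---|---|
| Visits 4-37 | 72.8% | 72.8% | 72.8% |
| Visits 7-37 | 79.4% | 79.7% | 79.9% |
| Visits 4-40 | 74.0% | 73.7% | 73.6% |
| Visits 7-40 | 80.0% | 80.0% | 80.0% |

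For visits 4-37, z = 2.802 × 11/12 = 2.568, and the power is Φ(2.568 − 1.960) = 72.8%. Including visit 4 costs about 6-7 percentage points.

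**Baseline adjustment.** With the visit 4 score as a covariate for the mean of visits 7-40, the residual variance is v(12) − r². At r = 0.5 this is 0.5417 − 0.25 = 0.2917, and power rises to 90%, 97% and over 99% for r = 0.3, 0.5 and 0.7. With the mean of visits 1 and 4 as the covariate, the residual variance is v(12) − r²/((1 + r)/2). At r = 0.5 this is 0.5417 − 0.3333 = 0.2083, and power is 95%, 99.5% and over 99.9%.

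**Group-by-time slope.** The same covariance was used, with r = 0.5 and generalized least squares. For an effect growing linearly from zero to an assumed 0.3 SD, the slope z is 2.99 with visits 7-40 and 3.37 with visits 4-40. For a constant 0.3 SD effect after visit 4, it is 0 with visits 7-40 and 1.33 with visits 4-40. Adding visit 4 therefore raises the slope statistic in both cases.

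**The case against.** The strongest reply is that the error is not written into the plan. No section says that visits 4-37 are averaged or that visit 4 is an outcome. The planned model has group, time and group-by-time terms, and the Study Summary describes polynomial time trends. In such a model a point near baseline can anchor the trajectory, and the slope figures bear this out. This stands: the dilution is conditional on an average contrast. The plan nevertheless names no contrast, and its own labelling puts visit 4 among the treatment-phase scores.

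Several stronger readings are tempting and are not supported:
- *One of 12 craving scores in every subject is untreated.* Visit 40 makes it 1 of 13 if that score is used. Section 6.4 also lets weekly assessments be done at any of the week's three visits, so a subject's first score may be taken after dosing starts. Prior-week recall is documented for the MCCS only.
- *Visit 4 creates an artificial group-by-time trend.* A divergence that begins at zero at the first dose is a real feature of the trajectory.
- *The visit 4 pill count is an error.* Section 6, item 14 records capsules dispensed as well as returned, and the dispensed number exists at visit 4. It should stay.
- *One of 36 treatment-phase urines is pre-treatment, so the primary outcome is affected in that proportion.* Hypothesis 1 models daily indicators built from urine and self-report, so a share of urines is not a share of that outcome.
- *The full gain from the fix measures the harm.* Suppose both analyses adjust for baseline, and visits 7-40 adjusted for visits 1 and 4 are compared with visits 4-37 adjusted for visit 1. The test statistic is then 1.21, 1.29 or 1.37 times larger for r = 0.3, 0.5 or 0.7. Only 12/11 = 1.09 of that is removed dilution; the remaining factors of 1.10, 1.18 and 1.26 come from the second baseline score.

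**Conclusion.** The point holds in a limited form. The plan labels visit 4 as treatment phase although an MCCS score taken at that visit looks back on the untreated week, and it leaves open both the role of visit 4 and the contrast for Hypothesis 3. If visit 4 is an outcome in an average group contrast, the loss is 7.7-8.3% of the effect, or about 6-7 percentage points from an assumed 80% power. This rests on a constant effect after the first dose, a visit 4 score that is fully pre-treatment, and no dropout. It barely depends on the correlation. The gain from baseline adjustment does depend on it, and the documents give no value.

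The bias is toward no effect, does not inflate the type I error, and concerns a secondary hypothesis. The change is worth making because it is nearly free.

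**What to change.** In Sections 6.4 and 7.2:
- State that the visit 4 craving scales are completed before the first dose, as an exception to the window that allows any visit of the week, and that they are baseline values.
- Flag any score from the visit 4 week that is taken after dosing starts, and do not use it as baseline.
- Adjust the craving models for baseline craving, using the mean of visits 1 and 4.
- Use visits 7-37 and 40 as the on-treatment scores. Assign each MCCS score to the week it recalls by actual date. Visit 40 procedures are also done at premature discontinuation, so those scores must not be placed in Week 13 by default.
- Name the contrast that tests Hypothesis 3: an average over the on-treatment scores, or a specified group-by-time contrast.

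No new assessment is needed, since all the scores are already scheduled. The cost is the wording, the dating rule and the order of procedures at visit 4.

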3. VITALS
4. CONMEDS
5. AE
6. CGIO
7. Pill count
8. Treatment Group Prediction Form visit 19

Research Staff

1. CCQ
2. CSSA
3. CGIS
4. TSR

5. MCCS
6. BSCS
7. MCP
8. DD
9. UDS
10. CO
11. Cotinine
12. UBT
13. BAL
14. TLFB
15. AE
16. ASI at visit 19
17. Treatment Group Prediction Form visit 19
18. UPT at visit 19 (females)
19. Any earned fishbowl draws completed and voucher earnings delivered

6.5 Second visit of each study week during randomized medication phase: Visit 5, 8, 11, 14, 17, 20, 23, 26, 29, 32, 35, 38

CBT Therapist

1. CBT Psychotherapy
2. CGIO
3. Treatment Group Prediction Form at visit 20

Research Staff

1. UBT
2. BAL
3. TLFB
4. AE
5. CO
6. Cotinine
7. Any earned fishbowl draws completed and voucher earnings delivered

6.6 Third visit of each study week during randomized medication phase: Visit 6, 9, 12, 15, 18, 21, 24, 27, 30, 33, 36, 39

Research Staff

1. UBT
2. CO
3. Cotinine
4. BAL
5. TLFB
6. AE
7. Any earned fishbowl draws completed and voucher earnings delivered

6.7 End of Randomized Medication Phase: Visit 40

Nurse or physician

1. PE
2. VITALS
3. EKG
4. CONMEDS
5. AE
6. CBC and blood chemistry including liver function tests (LFT) and CO2.
7. UA
8. CGIO
9. Pill count
10. Treatment Group Prediction Form

Research Staff

1. CCQ
2. CSSA
3. CGIS
4. TSR
5. MCCS
6. BSCS
7. MCP
8. DD
9. RAB
10. SCL-90-R
11. UDS
12. UBT
13. BAL
14. TLFB
15. ASI
16. Treatment Group Prediction Form (research technician and subject)
17. UPT(females)
18. Short Form Health Survey (SF-36)
19. CO
20. Cotinine

CBT Therapist

1. Treatment Group Prediction Form
2. CGIO

Diagnostician

1. HAM A
2. HAM D

7 Statistical Plan

7.1 Sample Size Determination

Power Analysis

Based on the results of our pilot trial (Plebani et al., 2011), we use the method described by Diggle et al. (1994) to estimate power, assuming a compound symmetry covariance structure. We assume a Type-I error level (Alpha level) of 0.05.

7.2 Statistical Methods

Data Analyses: The data analyses will be performed by [name], the CSA Statistician, and his staff. Prior to performing analyses, standard data screening/cleaning procedures will be applied (Tabachnik and Fidell, 2000). These procedures will (1) screen the data for data-entry errors, (2) check for outliers, (3) assess the extent and pattern of missing data, and (4) check that appropriate assumptions of Normality are met whenever necessary. Because of the size of the sample, it is unlikely that the randomization will result in significant imbalance of the distributions of demographic or other variables across the treatment groups. However, some additional covariates will be considered for inclusion in the analyses, to improve the precision of estimation for the treatment effects (Hauk et al., 1998). In particular, we will consider covariates describing levels of alcohol and cocaine use prior to the study. In all analyses, the assumptions underlying the application of all the statistical methods that are used will be examined, principally through the use of standardized residuals, influence diagnostics, and graphical displays.

Primary Hypotheses:

Hypothesis 1: The outcome of interest is cocaine use, measured with three-times-weekly urine benzoylecgonine (BE) levels and self-reports of use from the Time Line Follow Back, combined to yield daily use/no-use indicators for each study day. We will be examining both point prevalence and continuous cocaine abstinence. A generalized estimating equations (GEE) model will be used to model the effects of group and time on the log-odds of use across the treatment period.

The explanatory variables in these models will be a factor for group, and terms for time effects, and group by time interactions. In these models, we are interested in weekly rates of use, so time will be coded as weekly units, with up to seven daily indicators providing replications within a week. These models will provide valid estimates of the regression parameters (i.e. group and time effects) without requiring that the correlation between a subjects repeated urine drug screens is known. It is usually enough to specify a simple “working” correlation matrix, which need not agree with the true correlation matrix underlying the repeated measures. This provides a “robust” approach, but usually at the cost of larger sample sizes, and the lack of simple methods for comparing different models. Based on the work of Lipsitz,(Lipsitz et al., 1994), the sample size in this study will be more than adequate for the method to be valid. We will follow the recommendations of Pan and Connett (Pan and Connett, 2002) in selecting the working correlation matrix, and the recommendations of Pan (Pan, 2001a) in using an adjusted AIC statistic (his QIC statistic) to compare models. These analyses will be performed using PROC GENMOD in SAS.

Secondary Hypotheses:

Hypothesis 2 (effects of compliance with medication): The main analyses will be performed using an intent-to-treat (ITT) approach, so subjects will be analyzed according to their

assigned treatment, without reference to the level of treatment they actually receive. It is likely that some subjects will not comply with their assigned treatment, and that this non-compliance will be related to subject characteristics, and/or to unmeasured factors related to outcome. This non-compliance can diminish the extent to which the treatment groups are comparable with respect to measured and unmeasured variables. In this study, the placebo group will be unable to obtain varenicline, so non-compliance will probably result in underestimated treatment effects. We will gather information on compliance, and use it in further analyses to assess the sensitivity of the ITT analyses to the presence of non-compliance. The information will be obtained from weekly pill counts, on the basis of self-report and examination of blister packs.

Initially, we will use these sources to determine whether each subject has complied with their assigned medication for at least 80% of the trial. We will then include a binary variable indicating “80%” compliance in the analyses described above for Hypothesis 1, both as a main effect and as an interaction effect with varenicline group.

We will also use the sources described above to define variables representing compliance/non-compliance over each the 12 weeks of the treatment period. For the primary outcomes, we will perform extensions of instrumental variable regression analyses presented by Nagelkerke et al. (Nagelkerke et al., 2000). Here the instrumental variable is randomization and, under certain assumptions, will control for unmeasured bias when estimating the effect of varenicline relative to placebo in those who comply with their assigned treatment. These analyses will permit a more complete examination of the time-varying effects of compliance across the treatment period.

Hypothesis 3: The CCQ and MCC scales will provide weekly measures of cocaine craving. The scales provide a seven and a six-category Likert response, respectively, and it is likely that we will collapse some adjacent categories prior to the analyses, and regard the responses as ordinal. The analyses for these hypotheses will be perfectly analogous to those for Hypothesis 1, except that mixed-effects models for ordinal responses will be used (Hedeker and Mermelstein, 2000). These analyses will be performed using PROC NLMIXED in SAS.

Hypothesis 4: The CO and cotinine measures will be used to analyze dynamic changes in cigarette smoking, both in isolation and as they relate to cocaine use.

Other Analytic Issues:

Missing Data: For the longitudinal analyses described above, drop out from treatment and occasional missing daily use indicators will lead to incomplete data. The mixed effects and GEE models described above can make use of all available data provided by subjects, but the inferences drawn from them will be unaffected by the missing data only if the missing data can be regarded as ignorable, in the sense of Laird (Laird, 1988). In the current setting, this is implausible, and further analyses of the sensitivity of the mixed-effects and GEE models to the presence of missing data will be required. For the urine toxicology data, a simple approach, of frequent use in the current setting, is to assume that any missing urines are positive. While this is a reasonable starting point for analyses, it almost certainly overestimates the rates of use, and underestimates the variability about those rates, and further investigation through more formal analyses is required. We will use selection models to examine the effects of missing data (Kenward, 1998, Rotnitzky et al., 1998). We will explicitly model the probability of drop out at a time point as a function of baseline characteristics and responses at previous time points, using a logistic regression model, and incorporate the predicted probabilities into the main analysis. Any attempt to model the drop

out process requires us to make modeling assumptions about it, none of which can be tested on the observed data. While this was originally seen as a controversial aspect of the approach (Diggle and Kenward, 1994), it has become standard practice to perform the analyses under a range of different assumptions, and to assess the sensitivity of the results to them (Rotnitzky et al., 1998).

Additional Analyses: We will also collect and analyze some additional measures, of withdrawal severity, general clinical improvement (CGI), and external treatment (TSR). These variables are intended to provide a description of change in these areas across the course of the study. They will be used in analyses addressing possible mechanisms of treatment process, and will be included as time-varying covariates in the longitudinal analyses described above. Because we have no a priori hypotheses on their likely influence, and because there are selection issues regarding the interpretation of post-randomization change, we regard these analyses as exploratory and as hypothesis-generating for future studies.

7.3 *Subject Population(s) for Analysis*

- All-treated population: Any subject randomized into the study that received at least one dose of study drug

8 Safety and Adverse Events

8.1 *Definitions*

Adverse Event

An **adverse event** (AE) is any symptom, sign, illness or experience that develops or worsens in severity during the course of the study. Intercurrent illnesses or injuries should be regarded as adverse events. Abnormal results of diagnostic procedures are considered to be adverse events if the abnormality:

- results in study withdrawal
- is associated with a serious adverse event
- is associated with clinical signs or symptoms
- leads to additional treatment or to further diagnostic tests
- is considered by the investigator to be of clinical significance

Serious Adverse Event

Adverse events are classified as serious or non-serious. A **serious adverse event** is any AE that is:

- fatal
- life-threatening
- requires or prolongs hospital stay
- results in persistent or significant disability or incapacity
- a congenital anomaly or birth defect
- an important medical event

Important medical events are those that may not be immediately life threatening, but are clearly of major clinical significance. They may jeopardize the subject, and may require intervention to prevent one of the other serious outcomes noted above. For example, drug overdose

or abuse, a seizure that did not result in in-patient hospitalization, or intensive treatment of bronchospasm in an emergency department would typically be considered serious.

All adverse events that do not meet any of the criteria for serious should be regarded as ***non-serious adverse events***.

Adverse Event Reporting Period

The study period during which adverse events must be reported is normally defined as the period from the initiation of any study procedures to the end of the study treatment visit.

Preexisting Condition

A preexisting condition is one that is present at the start of the study. A preexisting condition should be recorded as an adverse event if the frequency, intensity, or the character of the condition worsens during the study period.

General Physical Examination Findings

At screening, any clinically significant abnormality should be recorded as a preexisting condition. At the end of the study, any new clinically significant findings/abnormalities that meet the definition of an adverse event must also be recorded and documented as an adverse event.

Post-study Adverse Event

All unresolved adverse events should be followed by the investigator until the events are resolved, the subject is lost to follow-up, or the adverse event is otherwise explained. At the last scheduled visit, the investigator should instruct each subject to report any subsequent event(s) that the subject, or the subject's personal physician, believes might reasonably be related to participation in this study. The investigator should notify the study sponsor of any death or adverse event occurring at any time after a subject has discontinued or terminated study participation that may reasonably be related to this study. The sponsor should also be notified if the investigator should become aware of the development of cancer or of a congenital anomaly in a subsequently conceived offspring of a subject that has participated in this study.

Abnormal Laboratory Values

A clinical laboratory abnormality should be documented as an adverse event if any one of the following conditions is met:

- The laboratory abnormality is not otherwise refuted by a repeat test to confirm the abnormality
- The abnormality suggests a disease and/or organ toxicity
- The abnormality is of a degree that requires active management; e.g. change of dose, discontinuation of the drug, more frequent follow-up assessments, further diagnostic investigation, etc.

Hospitalization, Prolonged Hospitalization or Surgery

Any adverse event that results in hospitalization or prolonged hospitalization should be documented and reported as a serious adverse event unless specifically instructed otherwise in this protocol. Any condition responsible for surgery should be documented as an adverse event if the condition meets the criteria for an adverse event.

Neither the condition, hospitalization, prolonged hospitalization, nor surgery are reported as an adverse event in the following circumstances:

- Hospitalization or prolonged hospitalization for diagnostic or elective surgical procedures for a preexisting condition. Surgery should **not** be reported as an outcome of an adverse event if the purpose of the surgery was elective or diagnostic and the outcome was uneventful.
- Hospitalization or prolonged hospitalization required to allow efficacy measurement for the study.
- Hospitalization or prolonged hospitalization for therapy of the target disease of the study, unless it is a worsening or increase in frequency of hospital admissions as judged by the clinical investigator.

